5 STUDY POPULATION

5.1 INCLUSION CRITERIA

Participants (patients, FCGs, and clinical hospice staff) will be recruited for both intervention and control arms.

FCG-Patient Dyads.

Patient - Eligible patients are newly admitted home hospice enrollees, aged ≥65 years old with: 1. advanced life-limiting illness; 2. an estimated life expectancy of >1 month; 3. recent functional status decline (defined as change in Karnofsky Performance Status [KPS]¹ to < 80% in prior 3 months); 4. polypharmacy (defined as ≥ 5 regularly scheduled medications [excluding antimicrobials]); 5. cognitive ability to provide informed consent based on a Short Portable Mental Status Questionnaire (SPMSQ) score ≥6² OR, with a legally authorized representative who is willing and able to provide proxy consent. These variables are easily assessed on hospice intake forms on admission.

FCG – FCGs are eligible if: they self-identify as “usually” or “always” providing care to the eligible patient; are English-speaking; have telephone access; and have cognitive ability to participate.³ Family is operationally defined “any relative, partner, friend or neighbor who has a significant personal relationship with, and provides a broad range of assistance.”⁴

Hospice Clinicians -

Hospice clinicians are eligible if : nurses, social workers, chaplains and medical directors deliver care or communicate with home hospice patients in the course of their primary hospice-related job responsibility; pharmacists are eligible if their primary responsibility is to oversee safety of prescribing of medications to home hospice patients or coordination of medication-related decisions with hospice prescribers.

5.2 EXCLUSION CRITERIA

A patient who meets any of the following criteria will be excluded from participation in this study:

1. Life expectancy of < 1 month
2. Age < 65 years old
3. Cognitively unable to provide informed consent AND no legally authorized representative (LAR) to who is willing to provide proxy consent

4. No family caregiver

5.3 LIFESTYLE CONSIDERATIONS

5.4 SCREEN FAILURES

We will not consent participants to do not meet eligibility criteria. It is possible that consenting, enrolled patients may die quickly after enrollment despite meeting eligibility criteria. This is not unexpected for this study population.

5.5 STRATEGIES FOR RECRUITMENT AND RETENTION

Patient and family caregiver participants will be recruited through the participating home hospice clinical sites. Each site minimally includes a dedicated Site Investigator and Research Assistant capable of enrolling in and conducting the study.

The total enrollment is up to 60 consenting patient-FCG dyads. Within each of the 2 hospice agencies, we will randomize 1 office to intervention and 1 to control status. Target enrollment is 15 FCG-patient dyads at each office (total 30 FCG-patient dyads per hospice agency).

Hospice clinician participants will be recruited at each hospice site. In cooperation with hospice administrative leaders, we will present the study to the hospice clinical teams and invite teams randomized to the intervention to complete the online education training intervention about medication review, education, and deprescribing.

The Site PI will develop study-specific recruitment strategies in consultation with the local hospice administration. Site RA and CRCs and other study staff will attend an introductory training program covering research related-communication, ethics, recruitment planning and implementation.

The screening and recruitment algorithms will be developed for each site, delineating expected processes and highlighting potential hurdles so that effective solutions can be developed. Key messages for the recruitment call/visit, supporting study diagrams, recruiting scripts, strategies for working with

bereaved family members, and simplified consent language will be developed. Tools will be practiced through role plays: refresher role plays will be repeated periodically during the study to ensure quality and consistency. Recruitment metrics will be monitored on a regular basis and will include screening eligibility, study completion, study withdrawal rates; progress will be presented to Site Investigators and staff. If a study site should encounter particular difficulty with enrollment, the study team may conduct a site visit to review obstacles and devise solutions, presenting results for review to the existing study stakeholder panel.

Site specific screening will follow this general scheme, but may be adapted (as described herein) to local workflow procedures to minimize impact on clinical care delivery:

In general, hospice staff (i.e. front-line hospice nurses or local administrative staff) will preliminarily screen eligible patients on their daily hospice census list and, at their discretion within the first week after the hospice admission visit, provide an *IRB-approved generic brochure* about research in hospice and palliative care; if there is interest in learning more about the study, the patient and family caregiver will also be given an IRB-approved study-specific brochure. A variation at some hospices routinely places an *IRB-approved generic brochure* about research in hospice and palliative care in the hospice admission packet along with information about how to contact the hospice to opt-out of being screened and contacted for research, or similarly routinely provides patients and families to opt-out of being screened for research based on the local hospice's forms and policies. We will work with local hospice leadership to identify the most appropriate approach for their system. Then, a list of eligible participants will be identified and confirmed by a CITI-trained RA who will examine the daily admissions for hospice to identify participants who meet eligibility criteria among patients who have indicated interest in hearing about the study to front-line staff (or, as applicable, has not opted-out to being screened for research). This will generate a final list of eligible patient and family, and the hospice will then forward contact information to the study team among eligible participants indicating in the form of an authorization to contact form.

The Site RA will follow-up to lead recruitment efforts.

6 STUDY INTERVENTION(S) OR EXPERIMENTAL MANIPULATION(S)

6.1 STUDY INTERVENTION(S) OR EXPERIMENTAL MANIPULATION(S) ADMINISTRATION

6.1.1 STUDY INTERVENTION OR EXPERIMENTAL MANIPULATION DESCRIPTION

Intervention: We will present the SPECTORx educational intervention to clinical hospice staff randomized to the intervention. This is comprised of 3 x 20-25 minute online in-service modules about systematic, patient-centered, medication review, educational support for family caregivers about medication administration, and deprescribing of potentially inappropriate medications. The intervention patient and family caregiver participants will be given a study-specific notebook including a blank notepad, a blank medication tracking sheet, and printed information about the Medications in Older Adult website, as well as printed guidance from the NIA's Medicine's and Medication Management website (<https://www.nia.nih.gov/health/topics/medicines-and-medication-management>) about "What Do I Need to Tell the Nurse and Doctor?", and clinical information handouts about medications commonly used in hospice (e.g. Haldol, Morphine, Understanding Nausea, Understanding Pain and Symptoms).

Attention control: We will refer clinical hospice staff randomized to control offices to "Medications in Older Adults" website sponsored by the American Geriatrics Society's Health in Aging Foundation. (<https://www.healthinaging.org/medications-older-adults>) Based on personal preferences, these materials can be shared via electronic link or the information can be printed and distributed in paper form to patients and their family caregivers. The attention control patient and family caregiver participants will be given a study-specific notebook including a blank notepad, a blank medication tracking sheet, and information about the Medications in Older Adult website.

At the end of the trial, staff in control offices will be offered the SPECTORx educational intervention training.

6.1.2 ADMINISTRATION AND/OR DOSING

Staff will be referred to this attention control resources one time, but will be able to access the resources as many times as they deem clinically appropriate for the care of their patients.

6.2 FIDELITY

6.2.1 INTERVENTIONIST TRAINING AND TRACKING

We will track completion of online learning of the three 20-25 minute SPECTORx educational modules, including self-assessment quizzes by tracking completion online and by asking consenting participants to complete brief self-assessments before and after the educational intervention. Study staff will periodically check in with hospice clinical staff to inquire about adherence to the study intervention. We will also track fidelity by asking FCGs of consenting hospice nurses brief questions about whether hospice staff conducted medication reviews, offered education and support about medication administration and management, and discussed the option of deprescribing medications that are potentially inappropriate.

6.3 MEASURES TO MINIMIZE BIAS: RANDOMIZATION AND BLINDING

Randomization is at the level of the office location within each hospice agency.

Outcomes assessments will be blinded with withholding intervention assignment data from the clinical research coordinator responsible for data collection related to the measurement of patient and family-caregiver outcomes and from the adjudication team responsible for measuring ADE and ADWEs.

6.4 STUDY INTERVENTION/EXPERIMENTAL MANIPULATION ADHERENCE

The intervention is a medication support care intervention delivered by hospice clinical team, led by the hospice nurse. Hospice teams are randomized to SPECTORx intervention or attention control of standard American Geriatric Society/NIA funded educational materials of medication management for older adults.

6.5 CONCOMITANT THERAPY

6.5.1 RESCUE THERAPY

7 STUDY INTERVENTION/EXPERIMENTAL MANIPULATION DISCONTINUATION AND PARTICIPANT DISCONTINUATION/WITHDRAWAL

7.1 DISCONTINUATION OF STUDY INTERVENTION/EXPERIMENTAL MANIPULATION

The study intervention, which targets hospice clinical staff, will be delivered one time at the beginning of the study and will be delivered to any new clinical staff joining the intervention site teams. We will inform the clinical sites of the end of the study when we 3 months after completion of study enrollment to allow for adequate, uncontaminated, collection of outcome data for all participants.

When a subject discontinues study procedures will be completed as indicated by the study protocol. If a clinically significant finding is identified (including, but not limited to changes from baseline) after enrollment, the investigator or qualified designee will determine if any change in participant management is needed. Any new clinically relevant finding will be reported as an adverse event (AE).

The data to be collected at the time of study intervention discontinuation will include the following:

- The reason(s) for discontinuing the participant from the intervention, and methods for determining the need to discontinue
- If the participant is due to complete assessments within 2 weeks of being discontinued from the study intervention, those assessments will be administered at the time of discontinuation; if the next scheduled assessments are more than 2 weeks from the discontinuation date, the discontinued participant will wait for the next scheduled assessment. Thereafter, the participant will be included in all future scheduled assessments, even though not participating in the intervention.

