| | 
• Family caregiver medication burden, as measured by the Family Caregiver Medication Administration Hassle Scale.• Family caregiver satisfaction with care, as determined by likelihood to recommend• Polypharmacy• Potentially inappropriate medication use, as determined by a modified Medication Appropriateness Index• Medication regimen complexity, as measured by the Medication Regimen Complexity Scale• Medication changes• Adverse drug withdrawal events, as measured by a single item single item measure of change in medication since last visit and associated symptom change• Patient Quality of life (QOL), as measured by the McGill QOL Questionnaire (MQOLQ)• Patient Symptoms, as measured by the Edmonton Symptom Assessment System (ESAS)• Performance status, as measured by the Karnofsky Performance Status sale (KPS)• Unanticipated Events (whether study-related or not), as measured by time to first important event, consisting of:
○ admission to a hospital for any reason○ admission to an emergency department for any reason |

- Overall survival, as measured by time-to-death

Endpoints*:

Primary Endpoint: Trial completion

Secondary Endpoints: As described in Secondary Objectives

Study Population:

Eligible participants are adults aged 65 years and older with advanced life-limiting illness with an estimated prognosis of 1-6 months who are prescribed 5 or more medications and their family caregivers.

Phase* or Stage:

Feasibility Trial

**Description of Sites/Facilities
Enrolling Participants:**

Hospice Sites. EOL practices vary regionally.¹³⁻¹⁵ Thus, we are partnering with two large, geographically distinct home hospice agencies to begin exploring the generalizability of SPECTORx nationally. Each agency has multiple offices serving different

local regions within their states. Care Dimensions (Massachusetts) has 2 offices serving 4 counties in Eastern MA, and CNS Home Health & Hospice (Utah) has 10 offices throughout Utah.

Description of Study Intervention/Experimental Manipulation:

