1.2 SCHEMA

1.3 SCHEDULE OF ACTIVITIES

| STUDY PERIOD | | | | | |
|--|---|---------|---------|------------------------|----------------------|
| TIMEPOINT | Screening / Post-allocation Enrollment | | | Close-out | |
| | 2 weeks | 4 weeks | 6 weeks | 8 weeks and monthly | 24 weeks or death |
| ENROLLMENT | | | | | |
| Eligibility screening | x | | | | |
| Informed consent | x | | | | |
| FEASIBILITY | | | | | |
| SPECTORx Intervention | | | | | |
| Attention Control | | | | | |
| ASSESSMENTS (Source/Items) | | | | | |
| FCG/Demographics | x | | | | |
| FCG/Family Caregiver | x | x | x | x | x |
| Medication Administration | | | | | |
| Hassle Scale | | | | | |
| FCG/Potential medication related symptom change | | x | x | x | x |
| FCG/Patient Centered Medication Communication | x | x | x | x | x |
| FCG/Satisfaction with Care (Likelihood to recommend) | | | | | x |
| EMR/ PT Demographics | x | | | | |
| EMR/ PT Primary Hospice Admitting Diagnosis* | x | | | | |
| EMR/ PT Comorbid Illness* | x | | | | |
| EMR/PT Medications* | x | x | x | x | x |
| EMR/PT KPS* | x | x | x | x | x |
| EMR/PT Survival* | | x | x | x | x |
| EMR/PT Health resource utilization (hospital admissions, emergency department visits)* | | x | x | | x |

| | | | | | |
|---|---|---|---|---------------------------|---|
| EMR/Potential Drug Related Problem Screen | x | x | x | x | x |
| Patient/Potential Drug Related Problem | | x | | x (& monthly thereafter) | |
| Patient/MQOLQ | x | x | x | x | x |
| Patient/ESAS | x | x | x | x | x |

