4.4 END-OF-STUDY DEFINITION

A FCG participant is considered to have completed the study if he or she has completed the baseline assessment, and at least the 2 week assessment and the post-death follow-up assessment (or at 6 months if patient survives 6 months after hospice admission).

A patient participant is considered to have completed the study if he or she has completed the baseline assessment, and at least the 2-week assessment.

The end of the study is defined as completion of the 6-month follow-up assessment shown in the Schedule of Activities (SoA), **Section 1.3**.

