8 STUDY ASSESSMENTS AND PROCEDURES

8.1 ENDPOINT AND OTHER NON-SAFETY ASSESSMENTS

The endpoint of the study is either patient death, disenrollment from hospice, or completion of 6 months of follow-up after study enrollment.

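### The end-of-study notice in 7.1 comes 3 months after enrollment closes although follow-up runs to 6 months, and 6.1.1 does not say which date governs the SPECTORx offer to control staff

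*Combined protocol and SAP*

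**What the plan says.** Section 7.1 sets the notice to sites: "We will inform the clinical sites of the end of the study when we 3 months after completion of study enrollment". It gives the reason as "to allow for adequate, uncontaminated, collection of outcome data for all participants". In the text available, words are missing after the second *we*, so the intended trigger cannot be read off. Three months is the only interval given.

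Follow-up is longer everywhere else:

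- The synopsis (1.1) gives 6 months per participant and 12 months from first enrollment to the end of data collection.
- The close-out column in 1.3 is headed "24 weeks or death".
- Section 4.4 states: "The end of the study is defined as completion of the 6-month follow-up assessment".
- Section 8.1 ends participation at death, hospice disenrollment, or "completion of 6 months of follow-up after study enrollment".

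Section 6.1.1 promises control-office staff the SPECTORx training when the trial ends. It gives no date and refers to neither 4.4 nor 7.1.

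On control materials, 1.1 describes an NIA handout, 4.2 refers control staff to the NIA medication website, 6.1.1 refers them to the American Geriatrics Society (AGS) foundation website, and 6.4 names AGS and NIA materials together. Section 6.1.1 lists printed NIA guidance in the intervention notebook only.

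**The concern.** A 3-month wait after the last enrollment cannot cover a 6-month follow-up window, so 7.1 does not deliver the protection for all participants that it gives as its reason.

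The date matters because the plan attaches the end of the study to two events up to 3 months apart: the last 6-month assessment (4.4) and the notice to sites (7.1). If an office took the notice as the signal for the 6.1.1 offer, control clinicians could learn the intervention while control dyads are still being assessed. If they also changed practice, the arms would become more alike late in follow-up. The effect size that 9.4.3 wants for planning the larger trial would then be pulled toward no difference. No test is at stake, because 9.2 already states that the trial lacks power for efficacy.

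**Working it through.** **Inputs from the documents.** 2 agencies × 2 offices × 15 dyads = 60, which reproduces the stated target; 30 are control. Follow-up is 6 months (8.1) or 24 weeks (1.3). The notice comes 3 months after enrollment closes (7.1). Post-baseline time points are weeks 2, 4, 6 and 8, then monthly to week 24. Reading monthly as every 4 weeks gives 2, 4, 6, 8, 12, 16, 20 and 24, eight in all.

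**Step 1, which needs no accrual assumption.** Three months is 3 × 365.25 / 12 / 7 = 13.0 weeks. The last-enrolled dyad has passed week 12 and has weeks 16, 20 and 24 to come: 3 of 8 time points and 6 − 3 = 3 months of follow-up.

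**Step 2, calendar.** The documents do not state the accrual length. A 12-month study less 6 months per participant implies 6 months. The notice then falls at month 6 + 3 = 9, and the 4.4 end of study at month 12.

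**Step 3, dyads in follow-up at the notice.** Assume uniform accrual over A = 6 months and exponential loss (death or disenrollment) with median m, so λ = ln 2 / m and S(t) = exp(−λt). Dyads enrolled in the last 3 months of accrual are between months 3 and 6 at the notice. The expected number still followed is (60/A) × [S(3) − S(6)] / λ.

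| Median (months) | S(3) | S(6) | λ | Dyads of 60 | Control, of 30 |
|---|---|---|---|---|---|
| 1 | 0.125 | 0.016 | 0.693 | 1.6 | 0.8 |
| 2 | 0.354 | 0.125 | 0.347 | 6.6 | 3.3 |
| 3 | 0.500 | 0.250 | 0.231 | 10.8 | 5.4 |
| 6 | 0.707 | 0.500 | 0.116 | 17.9 | 9.0 |

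The range of medians is an assumption, taken from the 1 to 6 month prognosis in 1.1. A 24-week window gives 1.5 to 15.5 dyads. Section 4.4 counts the caregiver's 6 months from hospice admission; with an assumed 2-week lag before enrollment the range is 1.5 to 15.4.

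**Step 4, share of assessments after the notice.** A visit at t months (t > 3) comes after the notice only for dyads enrolled in the last t − 3 months of accrual, a fraction (t − 3)/6. For weeks 16, 20 and 24, t is 3.68, 4.60 and 5.52, and the fractions are 0.113, 0.267 and 0.420. With median 3, S(t) is 0.427, 0.346 and 0.279. Expected visits after the notice: 60 × (0.113 × 0.427 + 0.267 × 0.346 + 0.420 × 0.279) = 15.5. The sum of 60 × S(t) over all eight visits is about 280, so the share is 5.5%. For medians 1, 2 and 6 the shares are 1.7/132.5 = 1.3%, 8.9/224.5 = 3.9% and 27.2/360.3 = 7.5%.

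**Step 5, sensitivity to accrual.** For A of 3 months or more, both results scale as 1/A. With 3-month accrual they double (3 to 36 dyads; 3 to 15% of assessments). With 9-month accrual they fall by a third (1 to 12 dyads; 1 to 5%).

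**Step 6, after the fix.** If the notice and the offer both follow the last dyad's end of follow-up, no dyad is in follow-up at either.

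**The case against.** The strongest reply is that contamination is inferred. Section 7.1 speaks only of telling sites that the study is ending. The training offer is in 6.1.1, and 4.4 formally defines the end of the study as the 6-month assessment. Read that way, no control dyad is exposed. Harm needs the offer to follow the notice, staff to take it up, and practice to change during follow-up, and no section states the first step. This stands: it is a risk left open by the wording.

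The second reply is size. The assessment share is an upper bound on dilution, because it treats every control clinician as trained and changed at once. For assumed standardized effects of 0.2 to 0.8, an 8% dilution is 0.016 to 0.064. The standard error of a standardized difference with 30 per arm, ignoring clustering and attrition, is √(2/30) = 0.26, and four offices make it larger. This also stands. The top of the range rests on a 6-month median, which has half the dyads outliving the longest stated prognosis.

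Two stronger readings are tempting:

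- A reader might infer that late enrollees are followed for only 3 months. That would touch the synopsis endpoint ("Primary Endpoint: Trial completion"), because 4.4 requires of the caregiver "at least the 2 week assessment and the post-death follow-up assessment (or at 6 months if patient survives 6 months after hospice admission". No section says that data collection stops at the notice, and 7.1 gives its aim as data for all participants.
- A reader might single out caregiver satisfaction ("FCG/Satisfaction with Care (Likelihood to recommend"), which appears to be marked only at close-out. The column positions in the extracted schedule are too uncertain to rest on. One late rating can also largely reflect care given before the notice.

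On the control materials, it is fair to say that 6.1.1 is the operative description and lists materials for both arms. The 4.2 text concerns staff referral, while the printed NIA guidance in 6.1.1 goes to dyads. A reader might conclude that the trial has no defined comparator, but that goes too far.

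**Conclusion.** The inconsistency is real and should be corrected. Step 1 shows, without any accrual or survival assumption, that the 3-month interval in 7.1 falls short of the follow-up in 1.1, 1.3, 4.4 and 8.1, and so fails its own stated purpose for late enrollees who are still being followed. Section 6.1.1 leaves open which date releases the training to control offices.

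The consequence is modest. Under uniform 6-month accrual and exponential attrition with a median of 1 to 6 months, about 2 to 18 of 60 dyads (1 to 9 of 30 control) are in follow-up at the notice, and at most about 1 to 8% of post-baseline assessments follow it. Accrual and attrition are assumptions, and shorter accrual raises both figures. Any dilution of the 9.4.3 planning estimate is small, and arises only if the offer follows the 7.1 date.

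The control-material conflict is a separate, minor point: four sections describe the materials differently.

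**What to change.** Complete the 7.1 sentence. In 7.1 and 6.1.1, state that the end-of-study notice and the control-office SPECTORx offer come only after the last enrolled dyad has reached death, disenrollment or 6 months, and cite 4.4 and 8.1. This is a wording amendment with no extra participants or assessments. Control offices may wait up to 3 more months for training.

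Separately, reconcile 1.1, 4.2, 6.1.1 and 6.4 to one list of materials per arm, for staff and for dyads, stating whether NIA material belongs to control, intervention or both. This too is wording only.
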